ESTIMATED DURATION OF SUBJECT PARTICIPATION IN THE STUDY:

The subjects will be tested on two separate occasions. Each session will take approximately two hours total time; however, the actual efficacy testing will take 60 minutes. There will be 4-14 days spacing between visits. A phone follow-up will occur 3 days (\pm 1 day) and 15 days (\pm 2 days) after the subject completes Sessions 1 and 2, respectively. If there are any adverse side effects, at the discretion of the PI, the subject may be asked to return to the study site for evaluation.

DURATION OF STUDY:

The study will be completed when the last subject completes the last follow up phone call. The expectation is that the study will be completed within 4-6 months of the first subject entry.

NUMBER OF SUBJECTS:

Up to 150 male and female subjects will be screened in order to enroll up to 76 ASA Category I or II subjects. The total number of exposures to study medication will be 152 (76 subjects x 2 exposures). Each of the CTY-5339-A treatment regimens will have 38 exposures and the CTY-5339-CB will have 76 exposures.

SAMPLE SIZE DETERMINATION:

The sample size was selected based on evaluating a reasonable number of subjects to determine whether CTY-5339-A has a longer duration of action than CTY-5339-CB, which contains 14.0% benzocaine only.

DOSAGE:

(specific gravity is slightly less than 1; therefore 200 μ L is an approximate volume.)

CTY-5339-A 1-metered spay = 200 mg total (\approx 200 μ L)
Benzocaine 28 mg + Tetracaine HCl 4 mg

CTY-5339-A 2-metered spays = 400 mg total (\approx 400 μ L)
Benzocaine 56 mg + Tetracaine HCl 8 mg

CTY-5339-CB = 200 mg (\approx 200 μ L)
Benzocaine 28 mg

INCLUSION CRITERIA:

- a. Male and female subjects between 18-75 years of age with a Body Mass Index (BMI) \leq 32;
- b. Subjects are ASA Category I or II and are in good physical health as judged by physical and laboratory examinations;
- c. Subjects with normal appearance of the oral mucosal tissues;
- d. At screening and at Baseline during Session 1, subjects with PPT scores on both cheeks of at least "3" (on a 10 point NRS) on the last 2 of 3 readings, 1 of which must be a score of at least "4";
- e. Subjects with mean QST Heat sensation temperature assessments

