Data will be generated as the difference in response between the control, non-treated site and the active treatment site within in each subject.

ANOVA and pairwise t-tests will be used to compare CTY-5339-A treatment groups to the CTY-5339-CB treatment group.

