8.4 Hypothesis

The following hypotheses will be tested to analyze the primary outcomes of the study:

- The null hypothesis that the duration of anesthesia (PPT and QST Heat) for the one spray CTY-5339-A group is the same as the corresponding duration for the CTY-5339-CB one spray group will be tested against the alternative hypothesis that the means are not equal.

The following hypotheses will be tested to analyze the secondary outcomes of the study:

- The null hypothesis that the duration of anesthesia (PPT and QST Heat) for the two spray CTY-5339-A group is the same as the corresponding duration for the CTY-5339-CB one spray plus CTY-5339-P one spray group will be tested against the alternative hypothesis that the means are not equal.
- The null hypothesis that the onset of anesthesia (PPT and QST Heat) for the CTY-5339-A groups is equal to the corresponding onset for CTY-5339-CB group will be tested against the alternative hypothesis that the means are not equal.
- The null hypothesis that the onset time until the first responder event (PPT and QST Heat) for the CTY-5339-A groups is equal to the corresponding onset time until a first responder event for CTY-5339-CB group will be tested against the alternative hypothesis that the event times are not equal.
- The null hypothesis that the duration time until the first non-responder event (QST and PPT) for the CTY-5339-A groups is equal to the corresponding duration time until the first non-responder event for CTY-5339-CB group will be tested against the alternative hypothesis that the event times are not equal.

The predicted outcome is that CTY-5339-A when locally applied to cheek mucosal tissue in the mouth will have an onset comparable to the fastest constituent, benzocaine, and a prolonged effect comparable to the longest acting constituent, tetracaine, of the combination product. The study also is designed to demonstrate that both the CTY-5339-A one and two-spray dosages are safe. (The assumption is made that benzocaine has a faster onset of action than tetracaine HCl.)

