9. SUMMARY OF STUDY DESIGN

This is a single-dose, double-blind and single-center study with an active control treatment. All subjects will remain at the study center for each of the two 60 minute test sessions. The volunteer subjects will be tested at two different test sessions separated by 4-14 days and serve as their own control.

The study will include 76 subjects with 60-minute evaluations at each test session.

At each session, a circular area of approximately 1 inch in diameter will be isolated on one side of the cheek. Each session will use a different side of the cheek. The possible sequences of treatments at the two sessions are:

Session 1		Session 2	
Formulation	Sprays	Formulations	Sprays
CTY-5339-A	1	CTY-5339-CB	1
CTY-5339-A	2	CTY-5339-CB	1
CTY-5339-CB	1	CTY-5339-A	1
CTY-5339-CB	1	CTY-5339-A	2

(To maintain double-blind conditions, the CTY-5339-CB subjects in two spray sequences will also receive one spray with the vehicle control (CTY-5339-P) just outside the circumscribed area. A third party not involved with evaluating subjects will administer the drug.)

For PPT, evaluations will be done at 1-minute intervals following drug administration for the first 5 minutes to capture onset of anesthesia. Starting at 5 minutes after drug administration, both PPT and QST will be done at 5-minute intervals up to the one hour time point. Once onset has occurred, if there is no analgesia at two consecutive evaluation time points (from 10 minutes onward), the session will be discontinued. In addition, if onset of analgesia has not occurred by 10 minutes post dose, the subject will be considered a treatment failure and no further assessments will be made.

PPT: The PPT will be assessed, using a 90-mm, 26-gauge pencil-point spinal needle (Polymedic or equivalent; Temena S.A., Bondy, France or its equivalent). At each post dosing time point, PPT will be assessed in 3 repetitions on the non-treated site using a 0-10 Numerical Rating Scale (NRS) with "0" as no pain and "10" as severe pain. PPT will then be assessed in 3 repetitions on the treated site. These assessments will be compared to the contra-lateral, non-treated site as "No pain", "Less Pain" or "Similar/More Pain". "No Pain" or "Less Pain" at an application site will be recorded as presence of analgesia/anesthesia ("Responder").

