13.5 Statistical Methods for Efficacy Evaluations

The primary efficacy analyses will be based on Modified Intent-to-Treat Population. The key comparisons will include:

1. CTY-5339-A, one spray versus CTY-5339-CB, one spray

The co-primary efficacy variables are duration of effect as measured by PPT and QST Heat. Duration of effect is defined as the time (in minutes) from onset to treatment failure (*i.e.*, for PPT, an assessment of “Same/More” pain, and for QST, the average heat temperature is greater than the average heat temperature at Baseline (non-treated cheek), up to the 60-minute time point (at two consecutive time points). For those discontinuing from the study for any other reason, the time to treatment failure will be censored at the last assessment time.

The secondary efficacy variables include:

- Duration of effect (PPT and QST) for CTY-5339A two sprays versus CTY-5339-CB, one spray plus CTY-5339-P one spray

- Duration of effect (PPT and QST) for CTY-5339A two sprays versus CTY-5339-A one spray
- Onset of anesthesia in minutes for PPT and QST Heat
- Percentage of responders at each time point for PPT and QST Heat for both onset and duration

Continuous variables will be analyzed via an ANOVA model with treatment effects at each of assessed time points. Pairwise comparisons for variables related to percentages will be analyzed via chi square tests. The 95% confidence intervals of the treatment differences will be presented using normal approximation with continuity correction, if appropriate. Pairwise comparisons for time-to-event related variables will be analyzed via a log rank model with treatment effects. Median time to event will be estimated and the 95% confidence intervals for the median will be presented, if appropriate.

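### One-spray A versus one-spray CB is a within-subject contrast with 38 planned pairs, but the plan names no paired analysis and does not say which test decides primary duration

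*Combined protocol and SAP*

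**What the plan says.** **Design.** Section 9 has each subject tested at two sessions "separated by 4-14 days and serve as their own control". In the sequence tables (synopsis and Section 9), every subject given one spray of CTY-5339-A in one session receives one spray of CTY-5339-CB in the other. Every subject given two sprays of A receives CB plus vehicle in the other. The synopsis counts are "Each of the CTY-5339-A treatment regimens will have 38 exposures and the CTY-5339-CB will have 76 exposures".

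**Tests.** Section 13.5 assigns methods by type of variable:
- Continuous: "Continuous variables will be analyzed via an ANOVA model with treatment effects at each of assessed time points".
- Percentages: "Pairwise comparisons for variables related to percentages will be analyzed via chi square tests".
- Time to event: "Pairwise comparisons for time-to-event related variables will be analyzed via a log rank model with treatment effects".

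The synopsis says "ANOVA and pairwise t-tests will be used to compare CTY-5339-A treatment groups to the CTY-5339-CB treatment group".

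**Primary endpoint.** Duration by pin prick and duration by QST heat are co-primary. Section 13.5 defines each as minutes from onset to treatment failure, and adds "For those discontinuing from the study for any other reason, the time to treatment failure will be censored at the last assessment time". Section 8.4 states the primary null hypothesis as equal duration, which "will be tested against the alternative hypothesis that the means are not equal". It lists a hypothesis on the time to the first non-responder event separately, among the secondary ones. Section 13.6 declares success if either co-primary endpoint is statistically significant at 0.05.

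**The concern.** There are two gaps.

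1. **The pairing is not used.** ANOVA with treatment effects, the ordinary t-test, chi-square and log-rank all treat the A and CB observations as coming from different people. If the two sessions of a subject are positively correlated, these tests overstate the standard error of the A minus CB difference. A real difference can then be missed, and confidence intervals come out too wide. The same holds for two-spray A against CB plus vehicle. It does not hold for two-spray A against one-spray A, which is a between-subject contrast and suits unpaired methods.

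2. **The deciding test is not named.** Duration is measured in minutes and is also a censored time, so two of the Section 13.5 rules can claim it. Section 8.4 and the synopsis point to means and t-tests, while the censoring rule points to log-rank. Success rests on one p-value, and the text as it stands would let the analyst choose the test after seeing the data.

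**Working it through.** **1. Number of pairs.** From the synopsis: 76 × 2 = 152 exposures; 76 / 2 = 38 for each A regimen; 38 + 38 = 76 for CB. This reproduces the stated counts. Each one-spray A subject also has a one-spray CB session, so the primary contrast has 38 planned pairs. No allocation ratio is given; the figure follows from the exposure counts and from keeping CB alone apart from CB plus vehicle, as the endpoint lists do.

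**2. Significance level.** Section 13.6: 0.10 / 2 = 0.05 per co-primary endpoint. Section 8.4 makes the tests two-sided. Section 13.1 gives no power, effect size or SD, so there is no planned power figure to reproduce.

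**3. Standard error.** With common SD σ and within-subject correlation ρ:
- true SE of the mean difference = σ√(2(1−ρ)/38)
- SE used by an unpaired test = σ√(2/38)
- ratio = 1/√(1−ρ)

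The documents give no ρ, so 0 to 0.7 is an assumed range. At ρ = 0.5 the ratio is 1/√0.5 = 1.41.

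**4. t-test power and size.** The assumed true difference is 0.5 SD. Paired power comes from the noncentral t with 37 df and noncentrality 0.5√38/√(2(1−ρ)); at ρ = 0.5 this is 0.5 × 6.164 / 1 = 3.08. Unpaired power and size come from 40,000 simulated trials of bivariate normal pairs.

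| ρ | SE ratio | Unpaired power | Paired power | True size of nominal 5% unpaired test |
|---|---|---|---|---|
| 0 | 1.00 | 58% | 57% | 5.0% |
| 0.1 | 1.05 | 58% | 61% | 3.9% |
| 0.3 | 1.20 | 59% | 72% | 2.1% |
| 0.5 | 1.41 | 61% | 85% | 0.7% |
| 0.7 | 1.83 | 63% | 97% | 0.1% |

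By normal approximation, the difference detectable with 80% power by a paired analysis is 2.80 × √(2(1−ρ)/38): 0.64 SD at ρ = 0, 0.54 at 0.3, 0.45 at 0.5 and 0.35 at 0.7.

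**5. Log-rank.** Assumptions: lognormal durations with means 31.25 and 25 minutes, CV 50%, ρ on the log scale, a 5-minute grid, observation to 55 minutes, no period effect, 5% censored under the alternative; 5,000 trials per cell. The clustered version sums score residuals within subject and uses a t reference on 37 df.

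| ρ | Plain, power | Clustered, power | Subject-stratified, power | Plain, size |
|---|---|---|---|---|
| 0 | 49% | 46% | 41% | 5.0% |
| 0.1 | 49% | 49% | 44% | 4.3% |
| 0.3 | 49% | 56% | 54% | 2.3% |
| 0.5 | 48% | 68% | 68% | 0.8% |
| 0.7 | 48% | 85% | 88% | 0.2% |

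The clustered test keeps its size at 4.1% to 5.2%, and the stratified test at about 5%.

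A separate simulation under different assumptions (CB median 20 minutes, hazard ratio 0.6, censoring at 60 minutes) shows the same pattern. Plain against clustered power is 50% against 50% at ρ = 0, 47% against 58% at 0.3, 49% against 71% at 0.5 and 50% against 85% at 0.7.

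**6. The recommended model.** A Cox model with treatment and period, subject-clustered variance and a t reference (1,200 trials per cell) had size of about 5% to 7% and power of 46%, 57%, 68% and 88% at ρ = 0, 0.3, 0.5 and 0.7.

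**The case against.** **The text under-specifies pairing but does not exclude it.** Nothing in Section 13.5 rules out a subject term, and pairwise could be taken to mean paired. But Section 13.5 attaches that word to chi-square and log-rank tests, where it means treatment against treatment, and the synopsis uses it for comparing treatment groups. The synopsis does describe a within-subject difference, but it is treated site minus non-treated site, not A minus CB. After dosing, QST is measured on the treated cheek only, so that difference cannot be formed for the QST endpoint.

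**Log-rank is the natural reading of Section 13.5.** This stands within that section: its ANOVA is applied time point by time point, while duration is one censored value per session. It does not settle the matter, because Section 8.4 puts the primary hypothesis on means, lists event times as a separate secondary hypothesis, and the synopsis names t-tests.

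**The loss depends on unsupported assumptions.** This stands. Pin prick is scored against the other cheek and QST against the session's own baseline, which may already remove some between-subject variation. At ρ = 0.1 almost nothing is lost. The log-rank gain also shrinks in harder settings. With 34% censoring (assumed means 45 and 56.25 minutes), plain against clustered power is 42% against 59% at ρ = 0.5 and 42% against 75% at 0.7. With an assumed 20% of sessions without onset scored as zero duration, it is 30% against 39% and 30% against 46%. The direction does not change.

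**It is a proof-of-concept study.** Section 13.1 accepts a clear trend and claims no power, so no stated operating characteristic is breached. Yet Section 13.6 still lets a p-value decide success.

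**The 38 pairs are planned, not guaranteed.** This also stands: enrolment is up to 76, and the mITT definition does not clearly require both sessions.

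**Conclusion.** The concern holds. The primary contrast is within-subject by design, and every test named for it is in standard use an independent-group test. The plan also supports two different primary tests for duration.

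With positive within-subject correlation the error is conservative, so its cost is power and precision. At 38 pairs and an assumed 0.5 SD difference, the t-test loses about 13 percentage points at correlation 0.3 (72 − 59) and 24 at 0.5 (85 − 61). The log-rank loss in the light-censoring setting is 7 points (56 − 49) and 20 points (68 − 48). These sizes depend on the assumed correlation, effect and censoring, none of which the documents supply; near zero correlation little is lost. The unnamed primary test is a defect at any correlation. The point should be fixed; it does not invalidate the design.

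**What to change.** In Section 13.5, name one primary test for duration that uses the pairing and handles censoring. One example is a Cox model with treatment and period terms, subject-clustered (robust) variance and a small-sample t reference, applied to the 38 subjects in the one-spray sequences. A subject-stratified log-rank test can serve as sensitivity analysis; it loses power at low correlation (41% against 46% for the clustered test at ρ = 0), so it is less suitable as primary. Then:

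- Use the same approach for two-spray A against CB plus vehicle.
- For continuous measures by time point, use a mixed model with a random subject effect and fixed treatment and period effects (cheek side optional).
- For within-subject responder percentages, use McNemar, conditional logistic regression or GEE.
- Keep between-subject methods for two-spray A against one-spray A.
- Align Section 8.4 and the synopsis with Section 13.5, so that the hypothesis and the test address the same quantity.

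The cost is analysis wording and programming. No new data or subjects are needed.

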mean Heat sensation threshold of 48.5°C or less, based on the last 2 of the 3 readings. Post-Baseline, the presence of analgesia/anesthesia will be defined when the heat sensation threshold at the treated site is higher than the Baseline (“Responder”).

All tests on the treated cheek will be done near the center of the circumscribed area, but in a slightly different place at each consecutive evaluation time point. All tests on the non-treated cheek will be performed at approximately the same part of the cheek as those on treated cheek.

Randomization: A randomization code will determine the sequence of treatments and to which circumscribed area the treatment is administered (left or right cheek). Sensory testing will be done in the following order: pin prick followed, where applicable, immediately by heat sensation tolerance.

Subjects retain the right to withdraw from the study at any time.

EFFICACY MEASUREMENTS

The primary comparison of interest is one spray of CTY-5339-A compared to one spray of CTY-5339-CB. Co-primary efficacy variables are duration of effect as determined by PPT and duration of effect as measured by QST Heat. Duration of effect is defined as the time (in minutes) from onset to treatment failure (for PPT, treatment failure occurs when an assessment of “Same/More” pain, and for QST, a treatment failure occurs when the average heat temperature is the same or less than the average heat temperature at Baseline up to the 60-minute time point (at two consecutive time points).

The secondary efficacy variables include:

- Duration of anesthesia (PPT and QST Heat) for the two sprays of CTY-5339-A compared to one spray of CTY-5339-CB plus CTY-5339-P
- Duration of anesthesia (PPT and QST Heat) for the two sprays of CTY-5339-A compared to one spray of CTY-5339-A
- Onset of anesthesia for PPT and QST Heat
- Percentage of responders for PPT and QST Heat for both onset and duration
- Percentage of responders for PPT and QST Heat at each time point

OTHER MEASUREMENTS

At Baseline and at the end of the 60-minute test session an ECG, vital signs, and a 7 mL blood draw will be taken. The blood will be analyzed for the occurrence of subclinical methemoglobinemia by the HUP – Pepper Lab via co-oximetry analysis. At screening and throughout each test session, subjects will also be monitored with pulse oximetry. Methemoglobinemia is being defined as >5% of a subject’s

hemoglobin in the methemoglobin state, or a pulse oximetry reading of less than 91%.

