QST: The heat stimuli are delivered in 3 repetitions, with inter-stimulus intervals of 30s. The basal thermode temperature is set at a comfortable 35°C. The rate at which the thermode heats up is set at 0.5°C/s, while the rate at which it cools down is set at 8°C/s. The maximum thermode temperature is set at 51°C. The first stimulus is disregarded and the remaining two stimuli are averaged for data analysis. In situations where a maximal analgesia/anesthesia effect is demonstrated in the initial two repetitions, the QST test will not be repeated for the third repetition and the data will be recorded as maximal effect (51°C) based on the first two repetitions.

Heat sensation threshold will be defined as the temperature at which the subjects first start to feel tingling, warmth, heat, or pain. All tests will be done near the center of the circumscribed area, but in a different place at each evaluation time point. For QST, the first time point after Baseline will begin at 5 minutes after drug administration. Subjects will have a hand held mouse that turns off the heat probe when they first start to feel tingling, warmth, heat, or pain. At the maximum heat level of 51° C, the heat probe turns off automatically. With a brief exposure at 51° C, there is no damage to the mucosal tissue.²⁵

Randomization: A randomization code will determine in which circumscribed area each treatment is administered (left or right cheek). Immediately prior to beginning each 60 minute test session, both the contra-lateral cheek and the cheek to be dosed will be evaluated with the PPT. For QST, the screening assessments will be performed on both cheeks, while during each treatment Session, at Baseline and all post-dosing time points, assessments will be performed on the treated cheek only.

Subjects retain the right to withdraw from the study at any time.

The PPT and QST tests will be done near the center of each evaluation area but in a different place at each evaluation time point. For PPT, the non-treated control cheek will always be tested before the treated area. The testing will be done in the following order where applicable: PPT and then QST.

A safety phone follow-up call will occur 3 days (± 1 day) after the Session 1 and 15 days (± 2 days) following Session 2.

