10.3 Assignment of Study Medication

Treatment assignments will be determined by a computer-generated randomization schedule maintained by the Statistics Group.

The randomization schedule will randomly assign one of the four treatments (CTY-5339-A one spray, CTY-5339-A two sprays, CTY-5339-CB one spray, or CTY-5339-CB one spray plus CTY-5339-P one spray) to the appropriate area(s) of the cheek mucosa. For PPT assessments, the untreated, control area on the contra-lateral side will always receive the stimulus assessment first.

Randomization numbers will be assigned in a sequential order starting from 101. A drug delivery team (different for the evaluators or other study personnel) will administer the treatments to the cheek mucosal area.

The randomization number assigned to the subject will be recorded in the CRF.

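### Sequence and treated cheek are randomised, but the efficacy analyses contain treatment only: add subject, session and cheek, and balance the list by sequence

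*Combined protocol and SAP*

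**What the plan says.** The design is a two-session crossover. Section 9 has subjects "tested at two different test sessions separated by 4-14 days and serve as their own control", and adds: "Each session will use a different side of the cheek". The synopsis states: "A randomization code will determine the sequence of treatments and to which circumscribed area the treatment is administered (left or right cheek". Section 10.2 says that the list fixes each subject's product for each session and the cheek to be treated. The synopsis and section 9 both tabulate the same four sequences.

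The analysis text does not use this structure. For continuous variables, section 13.5 says: "Continuous variables will be analyzed via an ANOVA model with treatment effects at each of assessed time points". For durations and onset times it says: "Pairwise comparisons for time-to-event related variables will be analyzed via a log rank model with treatment effects". The synopsis adds: "ANOVA and pairwise t-tests will be used to compare CTY-5339-A treatment groups to the CTY-5339-CB treatment group". No section gives a session, sequence, cheek or subject term, a stratum, or a sensitivity analysis that includes one.

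On allocation, the synopsis fixes exposures at 38, 38 and 76, but no section gives a number per sequence or per cheek, or mentions blocking. Section 9 mentions only the cheek in its randomisation paragraph ("A randomization code will determine in which circumscribed area each treatment is administered (left or right cheek"), and section 10.3 speaks of single treatments: "The randomization schedule will randomly assign one of the four treatments".

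**The concern.** A session effect is plausible in this design. In Session 2 the untreated pin-prick control cheek is the one that was sprayed, pricked and heated 4-14 days earlier, and the treated cheek is rated relative to it. The subject does the rating and has done the task before. The heat threshold depends on the subject's own button press, which practice can shift.

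A factor that is randomised but not modelled has two effects. It adds to the error of the treatment contrast. If it is unevenly spread over the treatments in the subjects analysed, it also moves the estimate. Balance is not secured in the text: no count per sequence or cheek is stated, the primary mITT set (section 13.2) drops subjects, and section 11.7 replaces some discontinued subjects and not others. Under section 13.6 the study succeeds if either co-primary duration reaches 0.05, so lost power or a shifted estimate bears directly on the go/no-go reading.

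**Working it through.** **The plan's own figures.** 76 x 2 = 152 = 38 + 38 + 76 exposures, and 0.10/2 = 0.05; both reproduce. The choice of 76 cannot be reproduced, because section 13.1 gives no effect, SD or power.

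**Inputs from the documents.** 38 subjects receive one-spray CTY-5339-A (synopsis), each with a CTY-5339-CB session. Tests are two-sided (section 8.4) at 0.05 per endpoint (section 13.6).

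**Assumed inputs.** Arm SD 15 min; within-subject correlation 0.5, so the SD of the A minus CB difference is 15 x sqrt(2 x (1 - 0.5)) = 15 min; true difference 7.5 min; session effect 5 min; side effect 5 min.

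1. *Unpaired comparison as written, order and side balanced.* Residual SD = sqrt(225 + 25/4 + 25/4) = sqrt(237.5) = 15.41, a rise of 2.7%. The smallest significant difference is 1.993 x SD x sqrt(2/38), which is 6.86 min at SD 15 and 7.05 min at SD 15.41. The mean difference has a true standard error of 15/sqrt(38) = 2.43. Power is roughly Phi((7.5 - 6.86)/2.43) = 0.60 without the two effects and Phi((7.5 - 7.05)/2.43) = 0.57 with them. Simulation gives about 0.60 and 0.58. Type I error is 0.01 or less, because the test ignores the positive correlation.

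2. *Omitting the subject.* At the same standardised difference (7.5/15 = 0.5 SD) and correlation, with no session effect, a simulation of 1,500 runs gave power 0.62 for the unpaired t-test and 0.86 for the within-subject analysis. This loss is much larger than that in step 1.

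3. *Paired analysis without the terms.* Variance inflation = (SD^2 + session^2 + side^2)/SD^2. Session only: 250/225 = 1.11. Both: 275/225 = 1.22. Noncentral-t power with n = 38 is:
   - no effects present: 85.1%
   - session effect unmodelled: 81.3%
   - both unmodelled: 77.5%
   - both fitted (35 instead of 37 degrees of freedom): 85.0%

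   The 77.5% averages over unrestricted order and side. With exact balance it is a little higher: (7.5 - 2.026 x sqrt(275)/sqrt(38))/2.43 = 0.84, or about 80%.

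4. *Range for step 3.* Over SD 12-20, session effect 3-8 and side effect 0-5 min, the inflation runs from (400 + 9)/400 = 1.02 to (144 + 64 + 25)/144 = 1.62.

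5. *Uneven order.* Bias = effect x (n2 - n1)/38. For a 5-min effect and a 23/15 split this is 5 x 8/38 = 1.05 min. If assignment were unrestricted 1:1, a split at least that uneven would have probability 0.256.

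6. *Type I error given a 14/24 split*, no true difference, simulated on a 5-min grid with a 60-min cap for the log rank:

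| Correlation | Session shift | Unpaired t | Paired t, no session term | Log rank | Within-subject with session |
|---|---|---|---|---|---|
| 0 | 0.5 SD | 0.075 | 0.066 | 0.067 | 0.047 |
| 0 | 1.0 SD | 0.134 | 0.100 | 0.133 | 0.047 |
| 0.5 | 0.5 SD | 0.021 | 0.079 | 0.032 | 0.047 |
| 0.5 | 1.0 SD | 0.071 | 0.126 | 0.085 | 0.050 |

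7. *Average type I error.* Over unrestricted randomisation with 5-min session and side effects, the paired t-test without the terms rejected in 0.048 of 40,000 null runs.

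**The case against.** The strongest objection is that the analysis in section 13.5 is unpaired, and there the missing session and cheek terms cost about two points of power (step 1). That stands. The 22% and the 78% against 85% apply only after the analysis has been made paired, and they should not be read as the loss under the plan as written.

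A reader might also infer that the omission biases the primary contrast or raises the false-positive rate. The documents do not support that. Chance imbalance has expectation zero and, on average, is already in the error variance (step 7). Bias needs both a real effect and an uneven split. In the example it is 1.05/2.43 = 0.43 of a standard error and about a fifth of the 5-min assessment interval.

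The design also blunts a session effect. Pin prick is scored against the other cheek in the same session, heat against the same cheek's baseline that day, pin-prick eligibility is rechecked on both cheeks at each baseline, and the room and team are constant (section 11.1). This limits shifts in sensitivity but does not exclude an effect on duration. For a left-right difference, the documents suggest no particular mechanism.

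Finally, a reader might infer from sections 9 and 10.3 that the randomised unit is undefined. The sequence tables and section 10.2 show that a list by session and cheek is intended, and the fixed exposure totals suggest that it was planned. What is missing is narrower: any stated balance by sequence or cheek. The 0.256 in step 5 is therefore an assumption about the list, not a property of it.

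**Conclusion.** The point holds as a matter of precision and of protection against uneven order or side. Sequence and cheek are randomised and vary within subject, yet no efficacy analysis contains session, cheek or subject.

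Under the assumed inputs, the unpaired analysis as written falls from about 0.60 to 0.58 in power when order is balanced, and the larger loss comes from omitting the subject. Pairing alone does not settle the matter: it leaves session and side effects in every difference, with 22% extra variance in the example (2-62% over the range tried). A 23/15 split adds 1.05 min of conditional bias, without raising the average type I error.

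All of these sizes rest on assumed SDs, correlation and effects. The power figures in steps 1 to 3 also treat duration as a normal variable, not as one capped at 60 min and read on a 5-min grid. The omission does not invalidate the study. The reason to act is that the correction is nearly free and removes a choice that would otherwise be made after the data are seen.

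**What to change.** **Section 13.5 and the synopsis.** Analyse pin-prick and heat duration and onset within subject, with subject, treatment, session (1 or 2) and treated cheek (left or right) as terms, in a mixed model or crossover ANOVA. Replace the unstratified log rank by a Cox model stratified by subject, or with a subject frailty, with treatment, session and cheek as covariates; a log rank test takes no fixed terms, so adding words to the present sentence would not be enough. Adding session and cheek to the present ANOVA without the subject would also leave the larger loss in place.

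**Section 10.3.** Replace "The randomization schedule will randomly assign one of the four treatments" by assignment to one of the four sequences tabulated in section 9, with 76/4 = 19 subjects each and the first-treated cheek balanced within sequence as nearly as possible (10/9). Word the randomisation paragraph of section 9 to match.

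**Cost.** Plan wording and two degrees of freedom (37 to 35 against a plain paired analysis). If neither effect exists, power goes from 85.1% to 85.0%. No new data are needed, because session and cheek are already on the randomisation list.
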